4.1.2 Definition of dose-limiting toxicities and stopping criteria

Dose-limiting toxicities will be determined during Cycles 1 and 2 of the dose-finding phase using CTCAE version 5. Toxicities that occur during the first 28 day cycle and meet the criteria below will be assessed for attribution to durvalumab monotherapy. Any of the below listed AEs encountered between Cycle 1 Day 1 and Cycle 2 Day 28 (ie, 56 day DLT monitoring period for combination therapy) and in the opinion of the Investigator is thought to be attributable to durvalumab or/and tremelimumab, given a reasonable possibility based on temporal exposure to IP and for which an alternate etiology does not exist or cannot be identified, will be classified as DLTs:

- Grade 5 toxicity
- Hematological toxicity: Any Grade ≥ 3 (including febrile neutropenia Grade ≥ 3) except for the following:
 - Grade 3 thrombocytopenia that does not result in a bleeding event or does not require platelet transfusion
 - Grade 3 neutropenia that resolves to Grade ≤ 2 within 7 days.
- Non-hematological toxicity:
 - Any Grade 4 imAE
 - Any \geq Grade 3 colitis
 - Any Grade 3 or 4 noninfectious pneumonitis
 - Any Grade 2 pneumonitis that does not resolve within 5 days to \leq Grade 1 after initiation of maximal supportive care (including use of steroids)
 - Any Grade 3 imAE, excluding colitis or pneumonitis, that does not downgrade to Grade 2 within 3 days after onset of the event despite optimal medical management including systemic corticosteroids and does not downgrade to \leq Grade 1 or baseline within 14 days of onset
 - Liver transaminase elevation $>5 \times$ upper limit of normal (ULN) or total bilirubin (TBL) $>3 \times$ ULN. For patients with liver metastases at baseline, transaminase elevation $>8 \times$ ULN will constitute a DLT
 - Grade 4 vomiting, diarrhea, electrolyte abnormality, or systemic reaction
 - Grade 3 toxicity lasting >7 days despite optimal supportive care
 - Any \geq Grade 3 non-imAE, except for the exclusions listed below
 - Any Grade 3 immune-mediated peripheral neuropathy or other immune-mediated neurotoxicity
 - Grade ≥ 3 inflammatory reactions.

The definition of DLTs excludes the following conditions:

- Grade 3 fatigue lasting ≤ 7 days.
- Grade 3 endocrine disorder (pituitary and/or adrenal insufficiency) that is managed with or without systemic corticosteroid therapy and/or hormone replacement therapy and the patient is asymptomatic.

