- Grade 3 hypothyroidism adequately treated with hormone replacement therapy.
- Grade 3 inflammatory reaction attributed to a local antitumor response (eg, inflammatory reaction at sites of metastatic disease, lymph nodes, etc.).
- Concurrent vitiligo or alopecia of any AE grade.
- Grade 3 infusion-related reaction (first occurrence and in the absence of steroid prophylaxis) that resolves within 6 hours with appropriate clinical management.
- Grade 3 fever (fever greater than 40°C [$>104^{\circ}\text{F}$] for $\leq 24\text{h}$ in duration).
- Any grade lymphopenia.
- Isolated Grade 3 electrolyte abnormalities that are not associated with clinical signs or symptoms and are reversed with appropriate maximal medical intervention (including supplementation) within 7 days of initiating supplementation.

Immune-related adverse events are defined as AEs of immune nature (ie, inflammatory) in the absence of a clear alternative etiology. In the absence of clinical abnormality, repeat laboratory testing must be conducted to confirm significant laboratory findings prior to designation as a DLT.

Guiding principles:

1. While the rules outlined above dictate the classification of AEs as DLTs, any other AEs that are observed during the observation period may be defined as a DLT in consultation with the DRC; after having taken into consideration the emerging safety profile of durvalumab and tremelimumab.
2. The NCI CTCAE (version 5.0) will be used for AEs reporting and its severity will be graded on a scale from 1 to 5 provided for each AE term.
3. An immune-mediated AE is defined as an AE that is associated with exposure to durvalumab or/and tremelimumab and is consistent with an immune-mediated mechanism of action after alternate etiologies have been considered and excluded.

4. In the absence of clinical findings, repeat laboratory testing must be conducted to confirm the clinical significance of abnormal laboratory test result before it is classified as a DLT.

Patient dosing or study enrollment may be halted in the dose-finding phase until the toxicity data can be further studied. If DLTs occur in $\geq 2/6$ patients on a given cohort, enrollment will be placed on hold and the DRC will be required to fully evaluate the available information prior to further patient enrollment. Upon review, a decision will be made to resume, stop or modify the study. If ≥ 2 DLTs occur at DL -1, the study may be prematurely stopped.

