In the dose-expansion phase, enrollment in a disease-specific cohort will be halted and the DRC will be required to fully evaluate the available information prior to further patient enrollment if $\geq 3/9$ patients have an AE or SAE that would be considered a DLT based on criteria established in the dose-finding phase. Upon review, a decision will be made to resume, stop or modify the study.

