8.3.7 Adverse events based on examinations and tests

The results from the Clinical Study Protocol mandated laboratory tests and vital signs will be summarized in the clinical study report (CSR). Deterioration as compared to baseline in protocol mandated laboratory values, vital signs, physical examination findings, or ECG should therefore only be reported as AEs if they fulfill any of the SAE criteria or are the reason for discontinuation of treatment with the IP.

If deterioration in a laboratory value/vital sign is associated with clinical signs and symptoms, the sign or symptom will be reported as an AE and the associated laboratory result/vital sign will be considered as additional information. Wherever possible, the reporting Investigator uses the clinical, rather than the laboratory term (eg, anemia versus low hemoglobin value). In the

absence of clinical signs or symptoms, clinically relevant deteriorations in non-mandated parameters should be reported as AE(s).

Deterioration of a laboratory value, which is unequivocally due to PD, should not be reported as an AE/SAE.

Any new or aggravated clinically relevant abnormal medical finding at a physical examination as compared with the baseline assessment will be reported as an AE unless unequivocally related to the disease under study, see Sections 8.3.9 and 8.3.10.

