8.3.13 Adverse events of special interest

An AESI is one of scientific and medical interest specific to understanding of the IP and may require close monitoring. An AESI may be serious or non-serious. The rapid reporting of AESIs allows ongoing surveillance of these events in order to characterize and understand them in association with the use of this IP.

Adverse events of special interest for durvalumab ± tremelimumab include but are not limited to events with a potential inflammatory or immune-mediated mechanism and which may require more frequent monitoring and/or interventions such as steroids, immunosuppressants and/or hormone replacement therapy. These AESIs are being closely monitored in clinical studies with durvalumab monotherapy and combination therapy. An imAE is defined as an AESI that is associated with drug exposure and is consistent with an immune-mediated mechanism of action and where there is no clear alternate etiology. Serologic, immunologic, and histologic (biopsy) data, as appropriate, should be used to support an imAE diagnosis. Appropriate efforts should be made to rule out neoplastic, infectious, metabolic, toxin, or other etiologic causes of the imAE.

If the Investigator has any questions in regards to an event being an imAE, the Investigator should promptly contact the Study Physician.

AESIs observed with durvalumab ± tremelimumab include:

- Diarrhea/colitis and intestinal perforation
- Pneumonitis/ILD
- Endocrinopathies (ie, events of hypophysitis/hypopituitarism, adrenal insufficiency, hyper- and hypo-thyroidism and type I diabetes mellitus)
- Hepatitis/transaminase increases
- Nephritis/blood creatinine increases
- Pancreatitis/serum lipase and amylase increases

- Rash/dermatitis
- Myocarditis
- Myositis/polymyositis
- Neuropathy/neuromuscular toxicity (eg, Guillain-Barré, and myasthenia gravis)
- Other inflammatory responses that are rare/less frequent with a potential immune-mediated etiology include, but are not limited to, pericarditis, sarcoidosis, uveitis, and other events involving the eye, skin, hematological, neuromuscular toxicities (eg, Guillain-Barré syndrome, myasthenia gravis) and rheumatological events.

In addition, infusion-related reactions and hypersensitivity/anaphylactic reactions with a different underlying pharmacological etiology are also considered AESIs.

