4.2.3.5 Physical examination

Physical examination findings will be reported as adverse events.

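### Protocol 8.3.7 keeps non-serious deteriorations in mandated laboratory tests off the AE page, while the DLT, AESI and expansion-hold rules count them as AEs, so AE-derived outputs can under-count them

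*Protocol*

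**What the plan says.** **Reporting rule.** Protocol 8.2.2 sends sites to 8.3.7 to learn when a laboratory result becomes an AE. There, deteriorations in mandated laboratory values, vital signs, physical examination findings or ECGs "should therefore only be reported as AEs if they fulfill any of the SAE criteria or are the reason for discontinuation" of study drug. The reason given is that mandated results are summarized in the study report anyway. The section goes on to require AE reporting of asymptomatic, clinically relevant changes in tests that are *not* mandated, so leaving out the mandated ones is deliberate. ALT, AST, bilirubin, creatinine, lipase, amylase and blood counts are all mandated (Tables 19 and 20; a site that routinely measures only one of lipase and amylase may use that one).

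**Rules that need these events as AEs.**
- Protocol 4.1.2 defines DLTs as "Any of the below listed AEs encountered between Cycle 1 Day 1 and Cycle 2 Day 28" that meet its criteria and are attributed to study drug by the investigator. The criteria include transaminase above 5 x ULN, bilirubin above 3 x ULN and most Grade 3 or higher hematological toxicity. It foresees purely laboratory DLTs: "In the absence of clinical abnormality, repeat laboratory testing must be conducted to confirm significant laboratory findings prior to designation as a DLT".
- The expansion hold in the same section applies when at least 3 of 9 "patients have an AE or SAE that would be considered a DLT based on criteria established in the dose-finding phase".
- Protocol 8.3.13 says AESIs may be non-serious and lists transaminase, creatinine and "Pancreatitis/serum lipase and amylase increases".

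**Physical examination.** The last paragraph of 8.3.7 says: "Any new or aggravated clinically relevant abnormal medical finding at a physical examination as compared with the baseline assessment will be reported as an AE". Its one exception is a finding clearly due to the disease. SAP 4.2.3.5 relies on that: "Physical examination findings will be reported as adverse events". The SAP amendment history shows that the physical examination listing was removed for this reason.

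**The concern.** Take a child with a confirmed, asymptomatic, drug-attributed ALT above 5 x ULN whose next dose is delayed but not stopped, and suppose that the event is not serious. It meets a 4.1.2 criterion and falls in an 8.3.13 category. Under 8.3.7 the site enters no AE.

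Immune toxicity that shows only in the laboratory is an expected pattern for this drug class, so the loss would be selective rather than random. What is at stake is the AE-based part of the safety results. Safety is a primary objective of dose-finding and the safety objective of expansion. Also at stake is the protocol's enrollment hold in a pediatric expansion phase, which is worded as a count of AEs.

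For physical examination the problem is simpler. If the first paragraph of 8.3.7 is followed, non-serious findings that do not end treatment reach no output at all, because the SAP no longer lists them.

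**Working it through.** The plan states no figure on this point, so there is nothing to reproduce. The check sets the texts side by side, then shows how sensitive the decision rules are.

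**1. Is there an exemption?** The only laboratory exception near 8.3.7 is potential Hy's law (8.3.8), which needs transaminase and bilirubin raised together. An isolated ALT, lipase or creatinine rise is not covered. Nothing exempts values that meet a DLT or AESI criterion.

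**2. Which outputs depend on an AE entry?**
- AESI tables are built from MedDRA terms of reported AEs, and immune-mediated AEs are classified from those AESIs (SAP 3.3.1).
- Causality, grade, dose-interruption, resolution and steroid-use outputs come from the same records (SAP 4.2.3.2).
- Investigator causality and action taken are collected per AE (Protocol 8.3.4 and 8.3.5). A DLT needs investigator attribution, so without an AE entry the DRC would have to obtain it another way.

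**3. Which outputs do not?** SAP 4.2.3.3 lists all laboratory data, highlights out-of-range chemistry and hematology values, and gives by-visit summaries, box plots, CTCAE shift tables and Hy's law tables. The shift list includes ALT, AST, bilirubin, creatinine and blood counts. It omits lipase and amylase, although both are mandated and are named AESI terms.

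**4. Expansion hold.** Protocol 4.1.2 counts an AE or SAE at 3/9 or more and says enrollment will be halted. SAP 1.2 counts safety events at 33% or more and says enrollment may be paused. The two differ in what is counted and in the consequence.

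**5. Sensitivity (illustration only).** Let p be the true per-patient probability of a DLT-type event, and f the share of affected patients whose only such event is laboratory-based and unrecorded. Both are assumptions; the documents give neither. The recorded rate is q = p(1 - f), and P(hold) = P(X >= 3) for X ~ Binomial(9, q).

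| p | f = 0 | f = 0.25 | f = 0.50 |
|---|---|---|---|
| 0.20 | 0.262 | 0.141 | 0.053 |
| 0.33 | 0.615 | 0.392 | 0.174 |
| 0.40 | 0.768 | 0.537 | 0.262 |
| 0.50 | 0.910 | 0.718 | 0.399 |

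For dose-finding, P(X >= 2) with X ~ Binomial(6, q) at p = 0.33 is 0.642, 0.460 and 0.259. Those values apply only if the DRC worked from AE entries alone, which the protocol does not say.

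**6. One event in STO.** AE tables use the safety set, not the evaluable set. With 10 evaluable patients and the stated 20% non-evaluable allowance, about 10 x 1.2 = 12 to 10 / 0.8 = 12.5 (so 12 to 13) are dosed. One missed event moves a rate by 1/12 = 8.3 to 1/13 = 7.7 percentage points.

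**The case against.** The strongest reply is that the plan does not lose the data. Laboratory evaluations are a safety endpoint in their own right, and 8.3.7 gives their separate summary as its reason for restricting AE entry. The DRC determines DLTs from the clinical database (Protocol 9.6.1), and the SAP reports DLTs as the DRC approved them (SAP 3.3.6). Dose delays and their reasons are summarized with exposure (SAP 4.2.3.7). The SAP's hold wording is not confined to AEs, and the DRC reviews safety data during expansion. Some laboratory events will be AEs anyway because they are serious, end treatment or carry a clinical diagnosis. How many depends on the AE definitions in Appendix B and the toxicity management guidelines, which are outside the text available for this check.

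Most of this stands, and it rules out three stronger readings:
- *The safety endpoints as a whole under-count.* They do not; only AE-derived outputs are exposed.
- *Dose-finding DLTs will be missed.* The documents give the DRC a route to them.
- *Lipase, amylase and TSH changes disappear.* They are listed and summarized by visit. TSH elevation is not itself a listed AESI; the thyroid AESIs are diagnoses.

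What it does not answer is the conflict of instructions. Shift tables carry no attribution, action taken or resolution, and cannot supply AESI or immune-mediated AE counts. The differing SAP hold wording is a further inconsistency, not a repair. The physical examination contradiction has no mitigating output.

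**Conclusion.** The conflict is real and in the current text. If sites follow 8.3.7, AESI, immune-mediated AE, causality and dose-interruption outputs will omit whatever non-serious, laboratory-only events occur, and the protocol's AE-based hold can miss them. DLT under-counting in dose-finding is a risk only.

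The size cannot be derived, because the documents give no frequency for such events. The bounds that can be stated are that one unrecorded patient turns 3/9 into 2/9 under the protocol hold, and that one missed event in STO is worth about 8 points. A reader might take 10 points from the 10 planned evaluable patients, but the AE tables use all dosed patients. The probabilities in the working rest on assumed p and f and on a hold judged from AE entries in exactly nine patients.

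The physical examination conflict within 8.3.7 stands without qualification.

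**What to change.** 1. **Protocol 8.3.7, first paragraph:** state that deteriorations in mandated laboratory values that meet a 4.1.2 criterion (in either phase) or fall in an 8.3.13 AESI category are reported as AEs whatever their seriousness.
2. **Visits already past:** last-patient-last-visit was estimated for Q1 2023 and the SAP's latest amendment is dated April 2023, so a site instruction alone may recover little. Derive counts of threshold-crossing values from the collected laboratory data and show them beside the AE tables.
3. **Expansion hold:** reconcile Protocol 4.1.2 with SAP 1.2 on what is counted and on the consequence. Which clinical rule applies is for the sponsor to settle.
4. **Physical examination:** remove these findings from the first paragraph of 8.3.7, so that its last paragraph and SAP 4.2.3.5 apply.
5. **SAP 4.2.3.3:** add lipase (high) and amylase (high) to the CTCAE shift tables.

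The cost is a short protocol amendment, somewhat more AE entries at sites, a derivation from existing laboratory data and two extra shift tables, with no new assessments. A TSH shift table, and AE entry for every laboratory change that leads to a delay or treatment, are optional and go beyond what reconciliation needs.

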8.3.8 Hy's law

Cases where a patient shows elevations in liver biochemistry may require further evaluation and occurrences of AST or ALT $\geq 3 \times$ ULN together with TBL $\geq 2 \times$ ULN may need to be reported as SAEs. Please refer to [Appendix D](#) for further instruction on cases of increases in liver biochemistry and evaluation of Hy's Law.

8.3.9 Disease under study

Events which are unequivocally due to disease under study should not be reported as an AE during the study unless they meet SAE criteria or lead to discontinuation of the IP.

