8.3.10 Disease progression

Disease progression can be considered as a worsening of a patient's condition attributable to the disease for which the IP is being studied. It may be an increase in the severity of the disease under study and/or increases in the symptoms of the disease. The development of new, or progression of existing metastasis to the primary cancer under study should be considered as PD and not an AE. Events, which are unequivocally due to PD, should not be reported as an AE during the study.

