8.3.12 Deaths

All deaths that occur during the study treatment period, or within the protocol defined follow-up period after the administration of the last dose of IP, must be reported as follows:

- Death clearly resulting from PD should be reported to the Study Physician at the next monitoring visit and should be documented in the CRF in the Statement of Death page. It should not be reported as an SAE.
- Where death is not due (or not clearly due) to progression of the disease under study, the AE causing the death must be reported to the Study Physician as an SAE within 24 hours. It should also be documented in the Statement of Death page in the CRF. The

report should contain a comment regarding the co involvement of PD, if appropriate, and should assign main and contributory causes of death.

- Deaths with an unknown cause should always be reported as an SAE. It should also be documented in the Statement of Death page in the CRF. A post mortem may be helpful in the assessment of the cause of death, and if performed, a copy of the post-mortem results should be forwarded to AstraZeneca Patient Safety or its representative within the usual timeframes.

Deaths occurring after the protocol defined safety follow-up period should be documented in the Statement of Death page. If the death occurred as a result of an event that started post the defined safety follow-up period and the event is considered to be due to a late onset toxicity to IP then it should also be reported as an SAE.

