8.4 Safety reporting and medical management

8.4.1 Reporting of serious adverse events

All SAEs have to be reported, whether or not considered causally related to the IP, or to the study procedure(s). All SAEs will be recorded in the CRF.

If any SAE occurs in the course of the study, then Investigators or other site personnel inform the appropriate AstraZeneca representatives within 1 day (ie, immediately but **no later than 24 hours** of when he or she becomes aware of it).

The designated AstraZeneca representative works with the Investigator to ensure that all the necessary information is provided to the AstraZeneca Patient Safety data entry site **within 1 calendar day** of initial receipt for fatal and life-threatening events **and within 5 calendar days** of initial receipt for all other SAEs.

For fatal or life-threatening AEs where important or relevant information is missing, active follow-up is undertaken immediately. Investigators or other site personnel inform AstraZeneca representatives of any follow-up information on a previously reported SAE within 1 calendar day (ie, immediately but **no later than 24 hours** of when he or she becomes aware of it).

Once the Investigators or other site personnel indicate an AE is serious in the electronic data capture (EDC) system, an automated email alert is sent to the designated AstraZeneca representative.

If the EDC system is not available, then the Investigator or other study site staff reports a SAE to the appropriate AstraZeneca representative by telephone. The AstraZeneca representative will advise the Investigator/study site staff how to proceed.

This study will use EDC for SAE submission. If we are talking of back-up method when EDC is down, then it will be using SAE or relevant form to be scanned and emailed to the appropriate AstraZeneca representative or faxed.

For further guidance on the definition of a SAE, see [Appendix B](#) of the Clinical Study Protocol.

Reporting of serious adverse events and adverse events of special interest for patients receiving treatment following the final DCO.

The timeframe, for SAE reporting to the AstraZeneca representative remains the same during the post-DCO period

Adverse events of special interest are to be reported at the time of diagnosis of the event.

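### Protocol 8.3.9 and 8.3.10 give opposite reporting instructions for non-fatal clinical events that are due to progression and are serious or stop IP

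*Protocol*

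**What the plan says.** Protocol 8.3.9 states: "Events which are unequivocally due to disease under study should not be reported as an AE during the study unless they meet SAE criteria". The exception in full reads "unless they meet SAE criteria or lead to discontinuation of the IP".

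Protocol 8.3.10, the next section, treats progression as a worsening of the patient's condition caused by the disease being studied: "It may be an increase in the severity of the disease under study and/or increases in the symptoms of the disease". It ends: "Events, which are unequivocally due to PD, should not be reported as an AE during the study". No exception follows.

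Three other sections bear on the same events:

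- Section 8.3.7 has a rule for laboratory results: "Deterioration of a laboratory value, which is unequivocally due to PD, should not be reported as an AE/SAE". For physical examination findings it requires a new or worsened finding to be reported "unless unequivocally related to the disease under study, see Sections 8.3.9 and 8.3.10". It sends the reader to both sections and does not rank them.
- Section 8.3.12 has a rule for deaths: "Death clearly resulting from PD should be reported to the Study Physician at the next monitoring visit". Such a death goes on the Statement of Death page and is not an SAE.
- Section 8.4.1 requires every SAE to be reported whatever its cause.

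SAP 4.2.3.2 tabulates patients with SAEs and with AEs leading to discontinuation, and separately those judged causally related. It has no rule to exclude, flag or separately present events due to disease or progression.

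**The concern.** Because 8.3.10 defines progression through the disease under study, an event due to progression is also an event due to the disease. A patient admitted for a symptom of a growing tumour has an event that 8.3.9 makes reportable and 8.3.10 forbids reporting. Two careful sites could record the same event differently, and both would be following the protocol.

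Safety is a primary objective in dose-finding and the safety objective in dose-expansion. About 20 centres in 7 countries supply the data (4.1). If they follow different sections, the all-cause SAE and AE-discontinuation percentages depend partly on local reading of the protocol, and nothing in the SAP would reveal it.

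**Working it through.** The plan states no figure on this point to reproduce. The check is a comparison of the rules, followed by a scale calculation.

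**Step 1. Apply each rule to each type of event unequivocally due to progression.**

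| Event type | 8.3.9 (8.4.1 for SAEs) | 8.3.10 | Own rule elsewhere | Result |
|---|---|---|---|---|
| Clinical, neither serious nor stopping IP | Not reported | Not reported | None | Agree |
| Laboratory deterioration | Reported if serious or stops IP | Not reported | 8.3.7: not an AE or SAE | Settled |
| Death | Reported | Not reported | 8.3.12: not an SAE | Settled |
| Non-fatal clinical, serious | Reported | Not reported | None | Conflict |
| Non-fatal clinical, stops IP | Reported | Not reported | None for AE reporting | Conflict |

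The conflict is confined to the last two rows.

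**Step 2. Ask whether such events can arise within the reporting window.** Patients have relapsed or refractory disease with no standard treatment left (5.1.1). The paediatric pembrolizumab study described in 2.2.1 had a median PFS of 1.8 months. Treatment continues between first progression and its confirmation (8.1), the combination may be restarted after progression (6.1.4), and AEs are collected until 90 days after the last dose (8.3.2). Much progression should therefore fall inside the window. How often it produces a serious or treatment-stopping event is not stated anywhere.

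**Step 3. Trace the outputs.**

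- The all-cause SAE and AE-discontinuation tables take whatever sites report, so they are exposed.
- The causally related versions should be largely protected, because an event unequivocally due to progression should not be attributed to IP.
- A DLT needs attribution to study drug with no alternate etiology (4.1.2), so DLT counts should be little affected.

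**Step 4. Scale.** If k patients have a progression event as their only qualifying event, the percentage moves by 100 × k / n.

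| n (Protocol 9.2) | k = 1 | k = 3 |
|---|---|---|
| 10, STO | 10.0 | 30.0 |
| 11, SARCOMA stage 1 | 9.1 | 27.3 |
| 26, SARCOMA maximum | 3.8 | 11.5 |
| 43, upper end of all dosed in expansion | 2.3 | 7.0 |

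The values of k are illustrative. The n of 10, 11 and 26 are planned evaluable patients. The safety set is all dosed patients, so its n may be somewhat larger and the shift somewhat smaller.

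**The case against.** The strongest reply is that 8.3.9 is the general rule and 8.3.10 the specific one, so 8.3.10 prevails. The progression-specific rules for laboratory results and deaths both point that way, and this may well be what was intended. It stands as a plausible reading. The protocol does not state it, however, and 8.4.1 points the other way for serious events. A site could also note that 8.3.10 says AE where 8.3.7 says AE/SAE, and conclude that SAEs remain reportable.

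A second reply is that 7.1 lists progression as a stopping criterion separate from AEs, so sites have a non-AE route for recording why treatment stopped. This stands, and it weakens the effect on the discontinuation table more than on the SAE table.

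Several stronger inferences are tempting but not supported:

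- **That progression deaths are a further contradiction.** Read alone, 8.3.9 would capture them, but 8.3.12 deals with them expressly.
- **That the SAE rate shifts by 11 to 22 points.** This comes from 0.9 × (0.2 to 0.4) × 0.6 = 0.108 to 0.216. The 0.9 treats the cited study's 12-month PFS of 10.2% as a progression rate in this trial's AE window, although it comes from another drug and counts deaths. The admission rate of 20% to 40% and the 40% background SAE rate appear nowhere in the documents, and the product assumes the two are independent. It also contrasts all sites following one section with all following the other, whereas mixed practice would move the rate less.
- **That progression is the commonest reason for admission.** No section gives reasons for admission.
- **That cohorts become non-comparable.** That would need site practice to line up with cohort, which nothing suggests.
- **That comparison with the adult combination SAE rate is lost.** The figure of about 15% in 2.3.2.3 is for drug-related SAEs, so its counterpart is the causally related table.

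**Conclusion.** The inconsistency is real and narrow. Two stated rules give opposite instructions for non-fatal, non-laboratory clinical events that are unequivocally due to progression and are serious or stop IP. No section reviewed ranks them. The conclusion rests on the wording alone and needs no assumed event rate.

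The consequence is mainly for two all-cause tables. Its size cannot be derived, but in cohorts this small one or two patients recorded differently would be visible. It does not undermine dose-finding decisions or the drug-related safety summaries. Appendix B, to which the protocol sends readers for AE and SAE definitions, was not available, so a clarification there cannot be excluded.

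**What to change.** First check Appendix B. If it does not resolve the point, reconcile 8.3.9, 8.3.10 and 8.4.1 into one reporting rule. Either of these would do:

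- State in 8.3.9 that its exception does not cover events unequivocally due to progression, which follow 8.3.10 and 8.3.12, and make 8.4.1 consistent.
- Copy the 8.3.9 exception into 8.3.10, excluding deaths due to progression.

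The sponsor should choose; the need is for a single rule. It still matters, because SAE reporting continues after the final data cut-off for patients on treatment (8.3.14).

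For data already collected under possibly mixed practice, add to SAP 4.2.3.2 a flag for events attributed to progression, and present the all-cause SAE and AE-discontinuation tables with and without them. The flag cannot recover events that sites did not report, so the report should say so.

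The cost is about one sentence in the protocol with matching CRF guidance, plus one flag and two repeat tables. The second option would also bring some additional SAE reports.
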